#### Exploratory Endpoints

960

- 961 • Postprandial incremental area under the glucose curve (4 hr)
- 962 • Peak postprandial glucose
- 963 • Times in ranges-overall and postprandial (70-180 mg/dL, >180 mg/dL, >250 mg/dL, 70-140  
964 mg/dL)
- 965 • Mean glucose
- 966 • Rate of hyperglycemia events, defined as 90 or more minutes >300 mg/dL within 120 minutes
- 967 • Overall variability (CV and SD)
- 968 • HbA1c change from baseline
- 969 • CGM metrics for hypoglycemia, hyperglycemia, and variability during daytime and nighttime

970 Patient-Reported Outcomes

- 971 • TRIM-D
- 972 • Trim-DD
- 973 • ITSQ

974 **8.5 Analysis Datasets**

975 For the main analyses, adult and pediatric participants will be pooled. Secondly separate analyses will  
976 be conducted for adults (>18 years) and pediatric (<18 years) participants. Further exploratory analyses  
977 will be conducted within pediatric subgroups.

978 All participants who initiate the Treatment Period and use the study device with the study drug will be  
979 included in the safety analyses.

980 For inclusion in the analysis of CGM metrics, participants must have at least 24 hours of CGM data  
981 during the Treatment Period.

982 **8.6 Statistical Methods**

983 **8.6.1 Analysis of the Safety Event Endpoints**

984 Safety events (ie, not including CGM defined events) will be tabulated for each type of event as the  
985 number of events per participant, the number of participants with > 1 event, and the rate of events per  
986 100 person-years.

987 Since study eligibility excluded participants with 2 or more severe hypoglycemia or DKA events in the  
988 prior 6 months, an unbiased comparison of the event rate during the Treatment Period with the pre-study  
989 event rate is not possible. Therefore, the severe hypoglycemia and DKA event rates will be compared  
990 with the T1D Exchange data, which reported the frequency of 1 or more severe hypoglycemia and DKA  
991 events in the prior 3 months according to age group; this will allow for age-matching with this trial. The  
992 proportion of participants with events during the Treatment Period will be compared with the T1D  
993 Exchange frequency using Barnard's exact test. Study endpoint will be met if severe hypoglycemia and  
994 DKA event rates are not significantly higher during follow-up compared with T1D Exchange frequency.

995 **8.6.2 Analysis of CGM Endpoints**

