996 CGM metrics will be computed for (1) 4 weeks pre-study (personal CGM), (2) Lead-in Period, and  
997 (3) Treatment Period. CGM metrics will be computed over 24 hours, during daytime (6am-11:59pm),  
998 during nighttime (12mn-5:59am), and during scheduled exercise and meal challenges.

999 The main statistical comparison will be made between the Treatment Period and the Lead-in Period. The  
1000 lead-in period time for analysis will exclude the day and night of the baseline exercise and meal  
1001 challenges. Additionally the Treatment Period will be compared with the pre-study CGM data.

1002 Linear mixed models will be used to test the change from pre-Treatment Period to Treatment Period.  
1003 Missing data will be handled by the method of direct likelihood, which assumes outcomes are missing at  
1004 random and estimates follow-up values via maximum likelihood. Sensitivity analyses will be  
1005 performed to assess the robustness of the results under different missing data assumptions.

1006 **8.6.3 Analysis of HbA1c and PRO Measures**

1007 Linear mixed models will be used to test the change in HbA1c and PRO scores from baseline to  
1008 13 weeks. Missing data will be handled by the method of direct likelihood, which assumes outcomes are  
1009 missing at random and estimates follow-up values via maximum likelihood.

1010 **8.7 Intervention Adherence**

1011 The following tabulations will be performed:

- 1012 • Sensor use—percent time of use
- 1013 • Closed loop system use—percent time of use
- 1014 • % time in different operational modes

1015 **8.8 Protocol Adherence and Retention**

1016 The following tabulations and analyses will be performed to assess protocol adherence for the study:

- 1017 • Number of protocol deviations
- 1018 • Flow chart accounting for all enrolled participants
- 1019 • Number of and reasons for unscheduled visits and phone calls
- 1020 • Number of participants who were enrolled but did not enter the Treatment Period and reasons
- 1021 • Number of participants who stopped treatment and reasons

1022 **8.9 Baseline Descriptive Statistics**

1023 Baseline demographic and clinical characteristics of the cohort of participants who initiate the Treatment  
1024 Period will be summarized in a table using summary statistics appropriate to the distribution of each  
1025 variable. Descriptive statistics will be displayed by treatment group for the following:

- 1026 • Age
- 1027 • Sex
- 1028 • Race/Ethnicity

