## 105 **6 Calculation of Endpoints**

### 106 **6.1 Safety Endpoints**

107 An event is defined as a severe hypoglycemic event if the event required assistance of another  
108 person due to altered consciousness, and required another person to actively administer  
109 carbohydrate, glucagon, or other resuscitative actions.

110 An event is classified as a DKA event if the following occur:

- 111 • Symptoms such as polyuria, polydipsia, nausea, or vomiting;
- 112 • Serum ketones >1.5 mmol/L or large/moderate urine ketones;
- 113 • Either arterial blood pH <7.24 or serum bicarbonate (or CO2) <15; and
- 114 • Treatment provided at a health care facility

115

116 For each of the endpoints listed in Section 5.1, the total number of events for each participant  
117 and the event rate per 100 person years will be calculated. Event rates will be calculated as the  
118 total number of events occurring after the start of the treatment period divided by the number of  
119 person years the participant was active in the study. The person years will be calculated as the  
120 number of days between the start of treatment period and either the 13-week visit date or drop  
121 out date divided by 365.25.

122 The proportion of participants with at least 1 or more severe hypoglycemia and DKA events will  
123 be compared with published T1D Exchange data matched by age group (<18 years and ≥18  
124 years) (Table 1). An overall proportion will also be compared with the expected proportions  
125 from the T1D Exchange population using weights derived from the age groups. Study endpoint  
126 will be met if severe hypoglycemia and DKA event rates are not significantly higher during  
127 follow-up compared with T1D Exchange frequency.

128 A sensitivity analyses will restrict to severe hypoglycemic events occurring during the treatment  
129 period which resulted in a seizure or loss of consciousness, and DKA events which resulted in  
130 inpatient hospitalization or prolongation of existing hospitalization.

131 Adverse events occurring in the treatment phase during periods where Humalog is used will be  
132 reported separately.

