## 133 **6.2 CGM Endpoints**

134 CGM metrics will be computed for three study periods: (1) Pre-study period, (2) Lead-in period,  
135 and (3) Treatment period. Metrics will be calculated over 24 hours, during the daytime (6:00 AM  
136 to 11:59 PM) and nighttime (12:00 AM to 5:59 AM) periods, and during postprandial periods.  
137 CGM data from periods during the treatment phase where Humalog is used will not be included  
138 in the calculation of CGM metrics.

139 CGM metrics during pre-study period will be computed when possible using 28 days of pre-  
140 study CGM data collected at enrollment. CGM metrics for the lead-in period will be calculated  
141 by pooling all CGM data collected in the last 16 days of the lead in period. If multiple lead-in  
142 periods were required, CGM metrics will only be computed for the most recent. Data collected  
143 from the start of the treatment period until the date of the 13-week visit will be used to calculate  
144 CGM metrics during the treatment period. For those who miss the 13-week visit, data collected  
145 from the start of the treatment period to the last date that data is available or 91 days after the  
146 start of the treatment period, whichever comes first, will be used to compute CGM metrics. At  
147 least 24 hours of CGM data during overall, daytime, nighttime, and postprandial periods must be  
148 available for metrics to be calculated during those periods. CGM metrics will not include  
149 daytime and following nighttime CGM readings on days with meal or exercise challenges; these  
150 will be analyzed separately as described in Section 8.4.

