$$\frac{\text{Raw Score} - \text{Lowest Possible Raw Score}}{\text{Range of Possible Raw Scores}} \times 100$$

253 If any items are unanswered the total score and subscale pertaining to that item will not be  
254 calculated.

255 **6.5.2 ITSQ**

256 Items on the ITSQ are scored on a 7-point Likert scale. The raw total score and subscale scores  
257 are computed by calculating the mean across all non-missing item scores. Scores are then  
258 transformed to a 0 to 100 scale by using the following formula:

259 
$$\frac{7 - \text{Raw Score}}{6} \times 100$$

260 At least 75% of items must be non-missing to calculate scores.

261 **7 Analyses Cohorts**

262 All participants who initiate the treatment and provide at least 24 hours of CGM data will be  
263 included in the analyses.

264 **7.1 Analysis Windows**

265 The central lab HbA1c measured at the end of the lead-in period must be collected within 21  
266 days before to 7 days after the Lyumjev training visit, and the HbA1c measured at the end of the

267 treatment period must be collected within 42 days before to 30 days after the 13-week target date  
268 (91 days after the Lyumjev training visit). HbA1c measurements collected outside the analysis  
269 windows will be treated as missing.

270 The PRO outcomes at screening must be collected prior to the Lyumjev training visit, and PRO  
271 outcomes at 13 weeks must be collected within 42 days before to 30 days after the 13-week  
272 target date (91 days after the Lyumjev training visit). PRO outcomes collected outside the  
273 analysis windows will be treated as missing.

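### SAP 7 applies a 24-hour CGM condition to its only analysis cohort, whereas protocol 8.5 puts every participant treated with the study device and drug in the safety analyses

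*SAP*

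**What the plan says.** SAP 7 (Analyses Cohorts) is one sentence. It begins "All participants who initiate the treatment and provide at least 24 hours of CGM data will be" and goes on to place these people in the analyses, without saying which analyses or in which period the 24 hours must fall.

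Protocol 8.5 (Analysis Datasets) keeps two matters apart. On safety: "All participants who initiate the Treatment Period and use the study device with the study drug will be" part of the safety analyses. On CGM: "For inclusion in the analysis of CGM metrics, participants must have at least 24 hours of CGM data", and the sentence ends by tying those hours to the Treatment Period. Protocol 8.9 defines the baseline table with no CGM condition: "Baseline demographic and clinical characteristics of the cohort of participants who initiate the Treatment" Period.

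The SAP sections that use the safety data (6.1, 8.1 and the adverse event part of 8.2) name no population of their own. SAP 6.1 computes person-time from the "number of days between the start of treatment period and either the 13-week visit date or drop" out date. SAP 6.2 has its own CGM minimum: at "least 24 hours of CGM data during overall, daytime, nighttime, and postprandial periods must be" available before a metric is calculated for that period. SAP 1 declares every analysis consistent with the protocol.

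**The concern.** Safety is the primary objective of this single-arm study. Severe hypoglycemia and DKA are compared with registry frequencies. Unanticipated device effects, other serious events and adverse drug reactions are only tabulated, so for them the table is the result.

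A programmer following SAP 7 literally, with the Treatment Period as the window, would drop any treated participant who has under 24 hours of CGM data. That could be someone who stopped almost at once, possibly because of an event, or someone whose CGM data were lost or never uploaded. The protocol requires that participant in the safety tables. With rare events, one omission can change an event type from observed to not observed.

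**Working it through.** There is no stated figure to reproduce; both documents say that the sample size does not rest on statistical principles. The check is a comparison of texts, followed by arithmetic on assumed event counts.

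**1. Who is in the safety tables**

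| | Protocol 8.5 | SAP 7 |
|---|---|---|
| Safety analyses | Started the Treatment Period and used device with drug | Started treatment and has at least 24 h of CGM data |
| CGM metrics | Also at least 24 h of CGM data in the Treatment Period | Same single cohort |
| Window for the 24 h | Treatment Period | Not stated |

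**2. How much the unstated window matters.** Protocol 2.5 requires at least 85% closed-loop use in the lead-in before treatment starts. If lead-in data counted, almost everyone would pass. If the Treatment Period is meant, as in protocol 8.5, the cohort loses anyone with under 24 hours after the switch to Lyumjev.

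**3. Effect on a rare-event table (assumed counts).** Protocol 2.1 allows up to 200 participants to start treatment. Suppose one has a given event and is also the one without 24 hours of CGM data. The exact (Clopper-Pearson) 95% intervals are:
- all treated: 1/200 = 0.50%, 0.01% to 2.75%
- SAP 7 cohort: 0/199 = 0%, upper limit 1 − 0.025^(1/199) = 1.84%

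**4. Effect on the pooled registry comparison.** From the Overall rows of SAP Table 1:
- N = 1313 + 3183 + 2445 + 2143 + 1976 = 11,060
- severe hypoglycemia: 62 + 155 + 138 + 157 + 189 = 701, or 6.34%
- DKA: 31 + 113 + 96 + 43 + 22 = 305, or 2.76%

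These are crude frequencies, not weighted to the trial's age mix. I used a two-sided Barnard test with the pooled score statistic and maximised the nuisance parameter within 4 standard errors of the registry proportion:

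| Endpoint | Last count not significant, n=200 | First count significantly higher, n=200 | After one exclusion with an event |
|---|---|---|---|
| Severe hypoglycemia | 19 (p = 0.069) | 20 (p = 0.036) | 19/199 (p = 0.066) |
| DKA | 10 (p = 0.057) | 11 (p = 0.021) | 10/199 (p = 0.055) |

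One exclusion changes the result only when the count is exactly 20 or exactly 11.

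**5. Effect on the age-group comparisons.** SAP 6.1 also compares within <18 and ≥18 years. The registry DKA frequencies are (31 + 113)/(1313 + 3183) = 144/4,496 = 3.20% and (96 + 43 + 22)/(2445 + 2143 + 1976) = 161/6,564 = 2.45%. The group sizes are assumptions. The enrolment minimums give 80 + 20 = 100 pediatric participants, and so 160 − 100 = 60 adults among 160 completers. By the same test, the first count significantly higher is:

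| DKA | Assumed n | First significant count | p |
|---|---|---|---|
| Adult | 60 | 4 | 0.042 |
| Adult | 80 | 5 | 0.036 |
| Adult | 100 | 6 | 0.027 |
| Pediatric | 80 | 6 | 0.032 |
| Pediatric | 100 | 7 | 0.034 |

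The count must again sit exactly on the threshold for one exclusion to matter, but these thresholds are far lower than the pooled ones.

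**The case against.** The best defence is a reading that reconciles the two documents. SAP 7 says who is included and expressly removes nobody. SAP 1 claims consistency with the protocol. SAP 6.1 counts events and person-time from treatment start to the final visit or dropout, with no CGM condition. An analyst who reads these beside protocol 8.5 would keep every treated participant. That is a fair account of the probable intention, but it does not repair the text. SAP 7 is the only cohort definition, and its subsection 7.1 deals with HbA1c and questionnaire windows, so the section cannot be read as confined to CGM.

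The second defence is size, and it largely stands. The 1/200 example needs the one participant with the event to be the one lacking CGM data, and nothing in the documents suggests that this happened. If everyone treated has 24 hours, the two cohorts are identical. Adverse event forms, Medical Monitor review and the suspension counts in protocol 6.6.2 carry no CGM condition.

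The 24-hour condition should not simply be deleted on the ground that SAP 6.2 already covers CGM metrics. SAP 6.2 is a calculation rule for each period. Protocol 8.6.2 states: "Missing data will be handled by the method of direct likelihood, which assumes outcomes are missing at" random. Under that method, a participant with lead-in data alone could enter the mixed models, although protocol 8.5 excludes that person from the CGM analysis.

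**Conclusion.** The mismatch is certain: the SAP states one rule where the protocol states two, and the SAP rule is wrong as written for the safety tables. The effect is probably nil or very small, so the point is minor. This assumes that the 24 hours refer to the Treatment Period and that few treated participants lack them; the documents give no number for the second.

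Three stronger inferences are not supported.
- A reader might infer that the safety conclusion is in doubt. One exclusion changes a registry comparison only when the count is exactly at the threshold.
- A reader might infer the opposite, that the thresholds all lie well above the 5 cases in protocol 6.6.2 and so could not be approached. That holds for the pooled comparison (20 and 11) but not for the age groups, where adult DKA starts at 4/60 or 5/80. Protocol 6.6.2 also describes suspension for a root cause analysis, not a ceiling on events.
- A reader might infer that every other analysis must move to the safety set. Protocol 8.5 names no set for HbA1c, patient-reported or insulin outcomes.

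**What to change.** Replace the sentence in SAP 7 with two definitions that follow protocol 8.5:

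1. **Safety set:** all who initiate the Treatment Period and use the study device with the study drug. Use it for SAP 8.1, the adverse event part of 8.2, and the Treatment Period safety tabulations in 10.1, 10.2 and 12.
2. **CGM set:** members of the safety set with at least 24 hours of CGM data in the Treatment Period. Use it for CGM metric analyses only.

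Keep the baseline table on all who initiate the Treatment Period, as in protocol 8.9. The flowchart needs no change: protocol 8.8 asks for a "Flow chart accounting for all enrolled participants", and SAP 8.5 already starts from the number enrolled.

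The cost is one short paragraph and no new data. SAP version 4.0 is dated after follow-up was complete, so the number of treated participants with under 24 hours of Treatment Period CGM data can be counted directly and reported with the change. If it is zero, no safety table changes.

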## 274 **8 Statistical Analyses**

### 275 **8.1 Key Safety Analyses**

276 The total number of events, number and proportion of participants who experienced at least one  
277 event during the treatment period and the rate of events per 100 person years will be tabulated  
278 for each outcome listed in Section 5.1. The proportion of SH and DKA events will be compared  
279 to proportions of events occurring in a similar time frame among participants enrolled in the T1D  
280 exchange. These proportions have been previously published [2].

281 Barnard's exact test will be used to test the difference in proportions. A two-sided p-value testing  
282 the null hypothesis of no difference in proportions will be reported. For unanticipated adverse  
283 device effects, adverse drug reactions, and serious adverse events, the total number, number and  
284 proportion of participants who experienced at least one event during the treatment period and the  
285 rate of events per 100 person years will be tabulated.

286 All analyses described in this section will be repeated restricting to only severe hypoglycemic  
287 events that were associated with a seizure or loss of consciousness. Summary statistics will be  
288 reported for key safety outcomes by age group (6-13, 14-17, 18-25, 26-49,  $\geq 50$ ).

### 289 **8.2 Secondary Safety Analyses**

290 The total number of any type of adverse event, number and proportion of participants who  
291 experienced at least one adverse event during the treatment period and the rate of adverse events  
292 per 100 person years will be tabulated. For the CGM metrics listed in Section 5.2, summary  
293 statistics for each metric will be reported during the pre-study, lead-in, and treatment periods.

294 The main analyses will compare metrics from the lead-in period to the treatment period, and  
295 additional analyses will compare the pre-study period to the treatment period. Linear mixed  
296 models including study visit as a fixed effect and clinical site as a random effect will be used to  
297 estimate the mean change from the lead-in period to the treatment period. Similar models will be  
298 used to estimate the change from the pre-study period to the treatment period. A point estimate,  
299 two-sided 95% confidence interval and two-sided p-value will be reported from the models. If  
300 residuals are highly skewed, then a transformation or non-parametric method will be used.  
301 Summary statistics for all secondary safety endpoints will be tabulated separately for pediatric  
302 and adult participants, and by more detailed age groups (6-13, 14-17, 18-25, 26-49,  $\geq 50$ ).

303 **8.3 Exploratory Analyses**

304 Linear mixed models including study visit as a fixed effect and clinical site as a random effect  
305 will test the change from the lead-in period to the treatment period for all exploratory CGM,  
306 insulin, and HbA1c endpoints. If a central lab HbA1c is not available at baseline the screening  
307 HbA1c will be used. Similar models will test the change from screening to the end of the  
308 treatment period for patient reported endpoints. A point estimate, two-sided 95% confidence  
309 interval and two-sided p-value will be reported from the models. If residuals are highly skewed,  
310 then a transformation or non-parametric method will be used. For CGM metrics, a similar model  
311 will be used to test differences between the pre-study period and the treatment period. All  
312 analyses will be replicated for daytime, nighttime, and postprandial CGM metrics. A sensitivity  
313 analyses will compare all 24 hour CGM metrics between the lead-in and treatment periods  
314 restricting to complete cases. Summary statistics for all exploratory endpoints will be tabulated  
315 separately for pediatric and adult participants and by more detailed age groups (6-13, 14-17, 18-  
316 25, 26-49, ≥50).

317 **8.4 Meal and Exercise Challenges**

318 Linear mixed models similar to those described in Section 8.3 will be used to test the change  
319 from the lead-in period to the treatment period in CGM and insulin metrics calculated during  
320 meal challenges where no bolus was taken. Summary statistics will be reported for metrics  
321 calculated during meal challenges where a half or full bolus was taken. The percentage of meal  
322 or exercise challenges with a hypoglycemic event will be calculated, but the % time <54 mg/dL  
323 and % time <70 mg/dL will not be computed due to the short timeframe. A similar model will  
324 compare metrics between the lead-in and treatment periods for exercise periods, and linear  
325 contrasts will be used to test the null hypotheses that metrics for all 3 exercise periods during the  
326 treatment period are not different from the metrics calculated during lead-in period. For binary  
327 outcomes, repeated measures logistic regression model will be used to compare lead-in and  
328 treatment periods. Summary statistics for all meal and exercise challenge endpoints will be  
329 tabulated separately for pediatric and adult participants and by more detailed age groups (6-13,  
330 14-17, 18-25, 26-49, ≥50).

331 **8.5 Protocol Adherence and Retention Analysis**

332 The following outcomes relating to protocol adherence and retention will be reported. Summary  
333 statistics appropriate to the distribution will be tabulated.

- 334 • A flowchart reporting the following:
  - 335 ○ Number of participants enrolled
  - 336 ○ Number of participants who completed the Humalog training visit
  - 337 ○ Number of participants who completed the Lyumjev training visit
  - 338 ○ Number of participants who completed/missed the 6-week visit
  - 339 ○ Number of participants who completed/missed the 13-week visit
  - 340 ○ Number of participants who dropped from the study between each visit
- 341 • Reasons for dropouts
- 342 • Number of protocol deviations

- 343 • Number of and reasons for unscheduled visits and contacts

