### 398 **10.5 Infusion Set Changes**

399 Appropriate summary statistics for the interval between infusion set changes will be tabulated.  
400 The intervals between infusion set changes will be categorized and the number and percentage in  
401 each category will be tabulated separately for the lead-in and treatment periods. Tabulations will  
402 be reported for the overall cohort and separately for pediatric and adult participants.

403 The mean number of infusion set changes per week will be calculated on a participant level and  
404 compared between the Humalog and Lyumjev periods using a linear mixed model with clinical  
405 site included as a random site effect. If residuals are skewed, then a transformation or non-  
406 parametric method will be used.

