## 407 **11 Subgroup Analyses**

408 Descriptive analyses of all safety, HbA1c, 24 hr-CGM and insulin outcomes will be performed  
409 within age groups (6-12, 14-17, 18-25, 26-49,  $\geq 50$ ). Additionally, time in range 70-180 mg/dL  
410 and time  $< 54$  mg/dL during lead-in and treatment periods will be compared within the following  
411 subgroups:

- 412 • Age
- 413 • Diabetes duration
- 414 • Education
- 415 • Sex
- 416 • Race/Ethnicity

- 417 • HbA1c at Screening
- 418 • Pre-study CGM time in range 70-180 mg/dL
- 419 • Humalog lead-in total daily insulin

420 For each subgroup the mean difference and 95% CI will be reported within each group.  
421 Interactions between the subgroup and change from the lead-in to treatment period will be  
422 assessed using repeated measures mixed effects linear regression models with subgroup, visit,  
423 and a subgroup by visit interaction term included as fixed effects and clinical site included as a  
424 random effect. If the subgroup variable is measured on a continuous scale, then the continuous  
425 version will be included in the model. Two-sided p-values for interaction will be reported.

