## 431 **13 Multiple Comparisons**

432 The key safety endpoints will not be corrected for multiple comparisons. For all other endpoints,  
433 confidence intervals and p-values reported will be adjusted using the adaptive two stage group  
434 Benjamini-Hochberg (TST GBH) method to maintain a false discovery rate of 0.05 [3]. For  
435 multiplicity adjustments outcomes will be grouped as follows:

- 436 • Secondary safety endpoints
- 437 • HbA1c, 24 hour, daytime, nighttime, and postprandial CGM outcomes (Lead-In vs.  
438 Treatment)
- 439 • 24 Hour, daytime, and nighttime CGM outcomes (Pre-Study vs. Treatment)
- 440 • CGM outcomes following meal and exercise challenges
- 441 • 24 hour, daytime, nighttime, postprandial insulin metrics
- 442 • Insulin outcomes following meal and exercise challenges
- 443 • Subgroup analyses
- 444 • Patient reported outcomes

445

446 **14 References**

- 447 1. Brouns, F., Bjorck, I., Frayn, K. N., Gibbs, A. L., Lang, V., Slama, G., & Wolever, T. M.  
448 (2005). Glycaemic index methodology. *Nutrition Research Reviews*, 18(1), 145-171.  
449 <https://doi.org/10.1079/nrr2005100>
- 450 2. Foster, N. C., Beck, R. W., Miller, K. M., Clements, M. A., Rickels, M. R., DiMeglio, L.  
451 A., Maahs, D. M., Tamborlane, W. V., Bergenstal, R., Smith, E., Olson, B. A., & Garg,  
452 S. K. (2019). State of type 1 diabetes management and outcomes from the T1D exchange  
453 in 2016–2018. *Diabetes Technology & Therapeutics*, 21(2), 66-72.  
454 <https://doi.org/10.1089/dia.2018.0384>
- 455 3. Benjamini YB, Yekutieli D: The control of the false discovery rate in multiple testing  
456 under dependency, 2001; *Ann Stat*, 29(4):1165-1188.

457

460 **Table 1. Frequency of Acute Complications in the 2016-2018 T1D Exchange Registry Cohort**

	6–12 years old		13–17 years old		18–25 years old		26–49 years old		≥50 years old	
	N	# ≥ 1 Event (%)	N	# ≥ 1 Event (%)	N	# ≥ 1 Event (%)	N	# ≥ 1 Event (%)	N	# ≥ 1 Event (%)
Frequency of ≥1 Severe Hypoglycemia Event in Prior 3 Months a										
Overall	1313	62 (5%)	3183	155 (5%)	2445	138 (6%)	2143	157 (7%)	1976	189 (10%)
Insulin Delivery Method										
Pump	973	39 (4%)	2134	67 (3%)	1585	78 (5%)	1442	85 (6%)	1243	114 (9%)
Injections	317	22 (7%)	967	83 (9%)	817	58 (7%)	656	71 (11%)	706	74 (11%)
CGM Status										
CGM user	414	14 (3%)	584	15 (3%)	424	17 (4%)	684	36 (5%)	577	39 (7%)
CGM non-user	899	48 (5%)	2599	140 (5%)	2021	121 (6%)	1459	121 (8%)	1399	150 (11%)

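### The lead-in-to-treatment models in SAP 8.2, 8.3 and 10.5 name only clinical site as random; fitted as written they ignore the pairing within participants and overstate the standard error of the change

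*SAP*

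**What the plan says.** SAP 8.2 covers the CGM hypoglycemia endpoints: "models including study visit as a fixed effect and clinical site as a random effect will be used to" estimate the mean change between lead-in and treatment, with similar models for pre-study against treatment. SAP 8.3 uses the same terms for the exploratory CGM, insulin and HbA1c endpoints ("Linear mixed models including study visit as a fixed effect and clinical site as a random effect") and similar models for the patient-reported outcomes. SAP 8.4 carries this over to the continuous challenge metrics: "Linear mixed models similar to those described in Section 8.3 will be used to test the change". In SAP 10.5 the weekly number of infusion set changes is "compared between the Humalog and Lyumjev periods using a linear mixed model with clinical" site as the random effect.

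Two other models are described differently. SAP 11 says that subgroup interactions will be "assessed using repeated measures mixed effects linear regression models with subgroup, visit" and their interaction, with site random. For binary challenge data, SAP 8.4 plans as follows: "outcomes, repeated measures logistic regression model will be used to compare lead-in and" treatment periods. Neither says which unit is repeated.

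SAP 8.2 and 8.3 add a fallback: if "residuals are highly skewed, then a transformation or non-parametric method will be used". Protocol 8.6.2 and 8.6.3 call for linear mixed models with direct likelihood for missing data and name no random effect or covariance.

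**The concern.** This is a single-arm study, so its CGM comparisons rest on each person serving as his or her own control. A model whose only random effect is site treats a participant's lead-in and treatment values as no more alike than values from two different people at that site. The large, stable differences between people then stay in the residual and are counted as error in the change.

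The result is intervals that are too wide and p-values that are too large. In an efficacy trial that might pass as caution. Here the secondary endpoints include % time below 54 and below 70 mg/dL, and the question is whether Lyumjev makes them worse. An inflated standard error hides such a worsening. The exploratory CGM, insulin, HbA1c and patient-reported comparisons lose precision in the same way.

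**Working it through.** **Inputs.** Model terms: SAP 8.2, 8.3 and 10.5. Two-sided 95% intervals: SAP 8.2. n = 160 completers: SAP 4. About 10–15 sites: Protocol Summary. The documents give no correlation, SD or power for these endpoints, so there is no planned figure to reproduce and ρ is assumed. It must be the correlation given site; the marginal correlation would slightly overstate the effect.

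**Standard errors.** Let σ² be the within-site variance, equal in both periods, with complete pairs. Each site then has equal numbers in both periods, the site effect cancels, and the estimated change is the mean paired difference under either model.

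- Variance reported by the site-only model: 2σ²/n
- Actual (paired) variance: 2σ²(1−ρ)/n
- Ratio of standard errors: R = 1/√(1−ρ)

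If the SDs of the two periods differ by a factor k, R = √[(1+k²)/(1+k²−2ρk)]. Unequal SDs are plausible for CGM, because lead-in metrics use at most 16 days and treatment metrics about 13 weeks.

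**Power.** An effect with 80% power in a paired analysis lies 2.80 true standard errors from zero (1.96 + 0.84). The site-only test rejects beyond 1.96R true standard errors, so its power is Φ(2.80 − 1.96R), before any false discovery rate (FDR) adjustment.

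| ρ (assumed) | R, k=1 | Power, k=1 | R, k=1.5 | Power, k=1.5 |
|---|---|---|---|---|
| 0.3 | 1.195 | 68% | 1.176 | 69% |
| 0.5 | 1.414 | 51% | 1.363 | 55% |
| 0.7 | 1.826 | 22% | 1.681 | 31% |
| 0.8 | 2.236 | 6% | 1.955 | 15% |

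At k = 1 the actual size of the nominal 5% test is 0.019, 0.0056 and 0.0004 at ρ = 0.3, 0.5 and 0.7. The reported interval is as wide as a paired analysis of 160(1−ρ) people would give: 80 at ρ = 0.5 and 48 at ρ = 0.7.

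**Absolute size.** In within-site SD units, with n = 160 and k = 1, the change detectable with 80% power is:

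- paired: 2.80√(2(1−ρ)/160) = 0.26, 0.22, 0.17, 0.14 at ρ = 0.3, 0.5, 0.7, 0.8
- site-only: 1.96√(2/160) + 0.84√(2(1−ρ)/160) = 0.30, 0.29, 0.27, 0.26

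**Simulation.** With 160 participants, 12 sites, site variance 0.1, within-site variance 1 and a site intercept only, the ratio of site-only to paired standard error was 1.189, 1.414, 1.802 and 2.223 at the same four values of ρ. Adding a participant intercept within site at ρ = 0.7 brought the standard error from 0.1114 to 0.0624, equal to the paired value. In a separate run (14 sites, site ICC 0.05) with 10% of follow-up missing at random, the ratios at ρ = 0.5, 0.7 and 0.8 were 1.36, 1.77 and 2.15 (k = 1) and 1.33, 1.63 and 1.89 (k = 1.5).

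**With FDR control (illustration only).** Under SAP 13, "confidence intervals and p-values reported will be adjusted using the adaptive two stage group" Benjamini-Hochberg method. The secondary family holds 13 lead-in comparisons by my count: 3 overall, plus 2 thresholds × 5 postprandial windows. I assumed a correlation of 0.5 between metrics, 3 to 13 real effects each with 80% unadjusted paired power, and a single-group two-stage procedure in place of the planned grouped one. Average power is 56–82% for a paired analysis. For the site-only model at ρ = 0.5, 0.7 and 0.8 it is 14–40%, 1–6% and under 1% (k = 1), or 18–46%, 3–14% and under 3% (k = 1.5).

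**Missing HbA1c or questionnaire values.** A model with no participant correlation cannot use the observed period to inform the missing one. With 20% missing (40 of 200) and an assumed 0.5 SD baseline gap, the bias is at most ρ × 0.20 × 0.5 SD, or 0.03 to 0.08 SD for ρ from 0.3 to 0.8. This is secondary.

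**The case against.** The best reply is that these descriptions are shorthand. The word 'including' need not introduce a full list. SAP 11 models the same change, calls it repeated measures, and still names only site as random, so in this SAP a site-only list may not imply independence within a person. SAP 10.5 names no period term either, so it cannot be complete. Direct likelihood has little content for a missing follow-up value unless the periods are correlated within person, and SAP 1 declares consistency with the protocol.

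This makes it plausible that a participant term was intended, and it is why the size is conditional. It does not put the term into 8.2, 8.3, 8.4 or 10.5. Two careful programmers could follow the same text and report standard errors that differ by a factor of 1.4 to 2.2 for ρ between 0.5 and 0.8.

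Several points about size stand. At low ρ the loss is mild, and at ρ = 0 there is none. The power figures concern small shifts, 0.14 to 0.26 SD, and the plan makes no power claim for them. The FDR figures rest on an approximate procedure and a uniform correlation, although the postprandial windows are nested, so they show direction rather than exact values. The error does not inflate false positives, and period summaries are reported anyway.

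The skewness fallback helps only in part. A transformed outcome stays in the same model, and the non-parametric option is not said to be paired.

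**Conclusion.** The concern holds for the model as written and should be fixed. SAP 8.2, 8.3 and 10.5, and the continuous models of 8.4 by reference, state no within-participant correlation, and no other section supplies it. SAP 11 and the binary model in 8.4 are only under-specified.

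For ρ from 0.5 to 0.8 the standard error of the change is inflated by 1.41 to 2.24 with equal SDs, or 1.36 to 1.96 at an SD ratio of 1.5; at ρ = 0.3 the factor is about 1.2. These figures assume complete pairs, a ρ that the documents do not give, and literal fitting of the stated terms. With complete pairs the estimated change itself is unaffected. The stated study endpoint, Barnard's test of severe hypoglycemia and DKA against the T1D Exchange, does not use these models.

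**What to change.** In SAP 8.2, 8.3, 8.4 (continuous metrics) and 10.5, keep visit fixed and site random, and add either a participant random intercept nested in site or an unstructured within-participant covariance, one and not both. In SAP 11 and the binary model of 8.4, name the participant as the repeated unit. State that any non-parametric fallback is a paired method.

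The cost is one phrase per model and one line of code. The SAP version history shows follow-up complete at version 4.0, so the change should be recorded as a dated clarification.
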